#### 12.2 Serious Adverse Events

A serious adverse event is an AE that:

- results in death
- is life-threatening i.e. the patient was at risk of death at the time of the AE
- requires inpatient hospitalisation or prolongation of existing hospitalisation
- results in persistent or significant disability/incapacity or
- is a congenital anomaly/birth defect
- requires acute medical or surgical care to prevent one of the outcomes listed above

# 12.3 Adverse Events of Special Interest:

An adverse event of special interest (AESI) is an adverse event for which on-going monitoring is appropriate within the context of the study. These events necessitate complementary examinations in order to characterize and understand them.

AESIs in this study can be related to:

- Hepatotoxicity
- Neurotoxicity/seizures
- Cutaneous reactions/photo toxicity

The study team, as well as the relevant referral facilities, should be trained to take particular notice of symptoms/signs suggestive of the AESIs in this study:

- 1) clinical and biological signs of possible hepatotoxicity such as:
- fatigue, nausea, abdominal pain, dark urine, putty or mastic coloured stools, jaundice (vellowing of the whites of the eyes or skin) and itching
- ALT value >5xULN or ALT value >3xULN AND total bilirubin value >2xULN
- 2) clinical signs of possible cardio-toxicity
- Palpitations
- Seizures
- Pounding/pain in the chest area
- Fainting/Syncope.
- 3) clinical signs of possible neurotoxicity/seizures such as:
- Seizures
- Dizziness
- Pins and needles sensations
- Visions disturbance
- Difficulties coordination
- Tinnitus
- 4) clinical signs of possible cutaneous reactions/photo toxicity such as:
- Urticaria
- angioedema
- · Skin lesions
- · Itching pruritus
- Discoloration
- Dermatitis

In all the cases of hepatotoxicity, confirmed by the PI / investigators, the sponsor. Notification will occur through the use of an ad hoc AESI form.

The patients with the following elevations may require more intensive inquiry on the part of the investigator: ALT value that exceeds 5.0 times the upper limit of normal or ALT value

that exceeds 3.0 times the upper limit of normal AND a total bilirubin value that exceeds 2 times the upper limit of normal (Hy's law).

The investigator should then consult the treating Cambodian physician to obtain an hepatitis panel (Anti-HAV IgM, Anti-HBc IgM, HBsAg, and hepatitis C RNA), hepatitis E IgM antibody, cytomegalovirus (CMV) testing polymerase chain reaction (PCR) testing, pp65 antigen, or IgM antibody; Epstein Barr virus (EBV) viral capsid antigen IgM antibody; In addition, serum creatinine phosphokinase (CPK) and lactate dehydrogenase (LDH) would need to be measured. The treating Cambodian physician will ensure proper referral in case a diagnosis of non-malaria or study drug related pathology.

#### 12.4 Pregnancy

In case of pregnancy, the anti-malarial treatment shall be the one recommended by the NMCP. The patient will not be included in the study.

Female patients will be encouraged to communicate to the PI if they will be pregnant within a period of two months after the start of the treatment.

The evolution of the pregnancy will be monitored with visits at 3, 6, 9 months and after the delivery. Information on the drugs taken during the pregnancy as well as AEs/SAEs and the health status of the newborn/s will be collected; thereafter the newborn/s will be followed at 6 and 14 weeks.

#### 12.5 Reporting Procedures for Adverse Events

#### Adverse Events

The AEs, regardless of their seriousness and causal relationship to the study drug, arising between the signature of the informed consent form and the last study visit (as per the protocol), must all be recorded on the patient chart (AE recording section). When possible, the symptoms must be regrouped within a single syndrome or diagnosis. The healthcare personnel shall have to specify the date of manifestation of the event, its intensity, final evolution, the measures taken and the treatment undertaken (if any).

#### Serious Adverse Events

In case of SAEs, the healthcare personnel will [name] within 24 hours for validation of the seriousness and determination of the causality. Subsequently, the following procedure will be followed:

• A signed and dated scanned copy of the "Adverse Event form" and the form "SAE

complementary information" will be send by email within 24 hours .

• The local responsible person for pharmacovigilance of the project will be informed within 72 hours.

The follow-up of each fatal or life-threatening AE will be provided to [name], the chariman of the DSMC, the local person responsible for the pharmacovigilance of the project. The information provided will include scanned, but anonymised, copies of the source data including detailed clinical, laboratory, and other relevant data.

# Follow-up of AE

The healthcare personnel must take all appropriate measures to protect the safety of the patients. Personnel must ensure to document follow-up of the evolution of each adverse event (clinical, biological or other) until resolution or until the stabilization of the patient's status.

All new relevant information concerning the initial SAE shall be recorded on a form "SAE follow-up information form" by the nursing staff of the health centre, and shall be validated by the PI / co-PI.

In case of a serious adverse event the patient must be followed until complete healing and normalization of all analysis results, or until chronicity of the patient's status. This can imply that the follow-up of the patient must continue beyond the period of follow-up per protocol, and that additional investigations could be requested by the sponsor.

#### 13. STATISTICAL ANALYSIS:

The primary analysis will be on an 'intention to treat' basis, including all patients enrolled into the study. Primary outcome will be the Kaplan Meier analysis up to day 42 of follow-up. A per protocol analysis will be based on all enrolled patients complying with all inclusion criteria who received a full course of the study drugs. Secondary analyses include the 'adequate parasitological and clinical response' (APCR) at day 28 and day 42. Safety and tolerability measurements will be summarized for the ITT patient population.

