# 7. Drugs and dosages

**Pyronaridine-artesunate** (Pyramax®, Shin Poong Pharmaceuticals). One tablet contains 60mg artesunate+ 180mg pyronaridine. Dosing will be according to body weight:

Body Weight(kg)	Daily dose(n	ng)	Number of tablets
	PYR	AS	
20-<24 kg	180	60	1 tab
24-<45 kg	360	120	2 tabs
45-<65 kg	540	180	3 tabs
65 ang above	720	240	4 tabs

Pyronaridine-artesunate will be taken orally with water, once daily for 3 days. Each dose will be administered under supervision in the clinic or if not possible by a home visitor to the patient's home. A dose will be repeated in full if vomiting occurs within 30 minutes of administration and halved if vomiting occurs between 30 minutes and 1 hour post dosing. This event will be documented in the case record form (CRF). Dosage tables are appended (Appendix 1).

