#### 8. Rescue treatment and treatment

If the patient vomits twice the treatment he/she will receive parenteral therapy based on the national treatment guidelines. If a patient is unable to tolerate the trial medication he/she should discontinue the treatment and alternative anti-malaria medication should be initiated. In this case, the reason for discontinuation should be recorded in the case record form (CRF) as "Adverse experience" and be withdrawn from the study. The patient will receive parenteral therapy with artemether or quinine 7 days (IV) + tetracycline 7 days as well as relevant supportive treatments.

Any patient with signs of severe malaria, will be hospitalized and receive parenteral therapy with artemether or quinine 7 days (IV) + tetracycline 7 days as well as relevant supportive treatments. Recurrent infections with *P. falciparum* will be treated with a 3-day course of artesunate+mefloquine (A+M) according to the national treatment guideline and the patients will be followed up for 42 days.

An episode of *P. vivax* malaria during follow up will be treated with dihydroartemisinin-piperaquine (DHA-PIP) according to the national treatment guidelines and the patients will be followed up over 28 days.

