# Early treatment failure

- danger signs or severe malaria on day 1, 2 or 3 in the presence of parasitaemia;
- parasitaemia on day 2 higher than on day 0, irrespective of axillary temperature;
- parasitaemia on day 3 with axillary temperature ≥ 37.5 °C;

• parasitaemia on day  $3 \ge 25\%$  of count on day 0.

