# APPENDIX 5. GUIDELINES FOR ANALYSIS OF RESULTS

	PCR-uncorr	ected results
End-point for day X (X = 28 or 42)	Cumulative success or failure rate (Kaplan-Meier analysis)	Proportion (per-protocol analysis)
Adequate clinical and parasitological response on day X	Success	Success
Early treatment failure	Failure	Failure
Late clinical failure before day 7	Failure	Failure
Late clinical failure or late parasitological failure on or after day 7	Failure	Failure
Other species infection	Censored day of infection	Excluded from analysis
Lost to follow-up	Censored last day of follow-up according to timetable	Excluded from analysis
Withdrawal and protocol violation	Censored last day of follow-up according to timetable before withdrawal or protocol violation	Excluded from analysis

	PCR-correcte	d results
End-point for day X (X = 28 or 42)	Cumulative success or failure rate (Kaplan-Meier analysis)	Proportion (per-protocol analysis)
Adequate clinical and parasitological response at day X	Success	Success
Early treatment failure	Failure	Failure
Late clinical failure before day 7	Failure	Failure
Late clinical failure or late parasitological failure on or after day 7		
falciparum recrudescence*	Failure	Failure

 
falciparum reinfection*
 
	Censored day of reinfection	Excluded from analysis
other species mixed with falciparum recrudescence	Failure	Failure
other species mixed with falciparum reinfection	Censored day of reinfection	Excluded from analysis

 
other species infection
 
	Censored day of infection	Excluded from analysis

 
undetermined or missing PCR
 
	Excluded from analysis	Excluded from analysis
Lost to follow-up	Censored last day of follow- up according to timetable	Excluded from analysis
Withdrawal and protocol violation	Censored last day of follow- up according to timetable before protocol violation or withdrawal	Excluded from analysis

\* WHO. Methods and techniques for clinical trials on antimalarial drug efficacy: genotyping to identify parasite populations. Geneva, World Health Organization, 2008 (http://www.who.int/malaria/resistance).

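### Section 13's full-course condition can drop from the per-protocol set an early treatment failure that Appendix 5 counts as a failure

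*Protocol*

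**What the plan says.** Protocol section 13 makes an intention-to-treat Kaplan-Meier analysis to day 42 primary. It then defines a per-protocol analysis on "all enrolled patients complying with all inclusion criteria who received a full course of the study drugs".

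Section 7 gives the course as "once daily for 3 days", and Table 1 places the doses on D0, D1 and D2.

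Section 10 allows early treatment failure to be met while dosing is still under way. One criterion is "danger signs or severe malaria on day 1, 2 or 3 in the presence of parasitaemia"; another is "parasitaemia on day 2 higher than on day 0, irrespective of axillary temperature". The remaining two criteria are assessed on day 3.

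Section 8 states: "Any patient with signs of severe malaria, will be hospitalized and receive parenteral therapy". Section 11 lists development of severe malaria among the reasons for which the investigator may withdraw a participant.

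Appendix 5 tabulates the handling of each outcome, with one column for Kaplan-Meier and one for a per-protocol proportion. In both the uncorrected and the PCR-corrected table the relevant row reads "Early treatment failure Failure Failure", that is, a failure in both columns. Late clinical failure before day 7 is scored in the same way. Neither row carries a dosing condition. Withdrawals and protocol violations are censored in the first column and excluded in the second.

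**The concern.** The protocol gives two rules for the per-protocol analysis and does not say which governs. Under section 13, membership depends on finishing the drug. A patient whose disease worsens during dosing and who is moved to other therapy does not finish it, so membership depends partly on the outcome. Under Appendix 5 the same patient is a failure.

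Removing such patients takes failures out of both the count of failures and the denominator, and so can only raise estimated efficacy. The direction is unwelcome in a study meant to find out whether the lower efficacy seen earlier in western Cambodia is genuine. It also matters that the per-protocol proportion is the only ACPR proportion Appendix 5 defines, while section 3 names PCR-corrected ACPR at days 28 and 42 as the primary endpoint.

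**Working it through.** **Can a patient fail before completing the course?** The doses fall on D0, D1 and D2. Taking the four early-failure criteria of section 10 in turn:

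- Danger signs or severe malaria with parasitaemia can be met on day 1 or 2, before the third dose. Section 8 moves patients with signs of severe malaria to parenteral therapy, so the course may be left incomplete.
- A day-2 count above day 0 can be met on the day of the third dose, but no section directs a change of treatment on this ground alone.
- The two day-3 criteria fall after the last scheduled dose, so they do not in themselves prevent a full course.

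The documented route is therefore severe malaria or danger signs on day 1 or 2.

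**How is that patient handled?**

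| Rule | Handling |
|---|---|
| Section 13 alone | Not in the set: no full course |
| Appendix 5, early-failure row | Failure |
| Appendix 5 applied within the section 13 set | Not in the set: already removed |
| Appendix 5, withdrawal row, if the patient is coded as withdrawn under section 11 | Excluded |

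Reading the two texts in sequence (set first, scoring second) does not cure the conflict, as the third line shows. The fourth line shows a further gap: nothing says whether the early-failure row or the withdrawal row takes precedence.

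A patient without a full course who has a late clinical failure before day 7 is in the same position: outside the section 13 set, but a failure under Appendix 5.

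**The plan's own figures.** Section 5 gives efficacy 90%, precision ±5 points, 138 patients, then 145 after 5% dropout. At a 95% level (assumed; not stated), n = 1.96² × 0.90 × 0.10 / 0.05² = 138.3, which agrees with 138. Then 138 × 1.05 = 144.9, giving 145.

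**Size.** Take 138 patients with an outcome. 0.90 × 138 = 124.2, so 124 successes and 14 failures. Let k of the 14 be failures who did not complete the course. The documents give no figure for k; 0 to 5 is an assumed range.

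- Appendix 5: 124/138 = 89.9% for every k.
- Section 13, with Appendix 5 scoring applied inside the set: 124/(138 − k).

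| k | Section 13 proportion | Difference from 89.9% |
|---|---|---|
| 0 | 124/138 = 89.9% | 0 |
| 1 | 124/137 = 90.5% | +0.7 points |
| 2 | 124/136 = 91.2% | +1.3 points |
| 3 | 124/135 = 91.9% | +2.0 points |
| 5 | 124/133 = 93.2% | +3.4 points |

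Differences are computed before rounding. The effect is about 0.7 points per patient.

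**The case against.** The best defence is that section 13 says who enters the set and Appendix 5 says how each outcome is scored, so the two complement each other. This stands for patients lost to follow-up. A reader might infer that section 13 keeps a fully dosed patient with no outcome in the denominator, so that 7 losses would give 124/145 = 85.5%, some 4.3 points below Appendix 5. The documents do not support that. Section 13 is silent on scoring such patients, and Appendix 5 supplies the rule: "Lost to follow-up Censored last day of follow-up according to timetable Excluded from analysis". Reaching 85.5% means counting losses as failures, which no section does; counting them as successes would give 131/145 = 90.3%, so even the direction is undetermined. If the per-protocol analysis is Kaplan-Meier, they are simply censored.

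The defence also disposes of a second inference: that a patient who breaches only an exclusion criterion stays in because section 13 mentions inclusion criteria alone. Appendix 5's protocol-violation row removes that patient.

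Third, the route is narrow. The day-3 criteria fall after the last dose, and a day-2 rise in count is not among the triggers for other treatment in section 8, so a switch on that ground cannot be assumed. That also stands, and it limits the likely number of patients.

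Fourth, a patient withdrawn for severe malaria might be excluded under Appendix 5 too, leaving no contrast. This is possible, but it depends on an order of precedence that the protocol does not give. It is a reason to state the order.

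The defence fails on the early failure itself. Once section 13 has removed the patient, no scoring rule applied afterwards can restore the failure.

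**Conclusion.** The contradiction is real but narrow. Section 13 can remove, because of the outcome, a treatment failure that Appendix 5 counts. The bias is upward, at about 0.7 points of per-protocol efficacy per patient, set against a planned precision of ±5 points. The size rests on 138 evaluable patients, 124 successes and an assumed number of affected patients, which is probably small. It also assumes that the move to parenteral therapy leaves the study course incomplete, which section 8 implies but does not state.

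The conflict does not reach the primary intention-to-treat Kaplan-Meier analysis. That analysis includes all enrolled patients, and its column in Appendix 5 scores early failure as failure with no dosing condition. The documents do not support any wider claim about lost patients or exclusion criteria.

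**What to change.** Replace the per-protocol sentence in section 13 with a definition that says three things:

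1. The per-protocol set is all enrolled patients who met all eligibility criteria and who either received the full course or met a treatment-failure criterion before completing it.
2. A failure criterion met before or at withdrawal is scored as failure and takes precedence over the withdrawal exclusion.
3. All other outcomes (loss to follow-up, other withdrawals and violations, reinfection, other species, undetermined or missing PCR) are handled as in the Appendix 5 tables.

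The first item should cover any treatment failure, not early failure alone. Otherwise an incompletely dosed patient with late clinical failure before day 7 would still be lost. The third item should defer to Appendix 5 and not simply require a classified outcome, because a PCR-confirmed reinfection is classified, yet Appendix 5 excludes it from the corrected proportion.

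The cost is a few lines of text. No new data, visits or patients are needed, and the change concerns only how outcomes are counted, not how patients are managed.

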#### 14. Quality assurance/quality control procedures

All blood slides from day 0, 3, 7, 21, 28, 42 and those from any return day will be validated by a CNM expert-level technician and also.

#### 15. Study drugs

#### 15.1 Storage

All efforts will be made to store the study drugs in accordance with the manufacturers' recommendations in a secure area. This may be difficult at some sites where air conditioned storage rooms are not available. The ACTs should be stored between 15°C to 30°C (59°F to 86°F).

# 15.2 Accountability of the study treatment

All movements of study medication will be recorded. Both individual subject and overall drug accountability records will be kept up to date by the study staff.

#### 16. Concomitant Medication

Throughout the study, investigators may prescribe any concomitant medications or treatments deemed necessary (e.g. antipyretics or anti-emetics) to provide adequate supportive care except for antibiotics with antimalarial activity unless unavoidable (e.g. doxycycline, azithromycin). If these are required the patients will be kept in the study and this will be noted as a protocol deviation. Antimalarials for recurrent infections will be prescribed as described above. Haematinics and anti-helmintics may be prescribed after day 7 if indicated. Any medication, other than the study medication taken during the study will be recorded in the CRF

#### 17. Monitoring

Study sites have in place a system for internal monitoring. Data will be evaluated for compliance with the protocol and accuracy in relation to source documents. The monitors will check whether the clinical trial is conducted and data are generated, documented and reported in compliance with the protocol, GCP and the applicable regulatory requirements.

A data safety monitoring committee (DSMC) will be overviewing the trial. The DSMC will be headed by an independent chairman, and also include an independent statistician and one additional independent member. Their remit will be defined in the DSMC charter (appendix).

#### 17. Ethics

The Investigator will ensure that this study is conducted in compliance with the current revision of the Declaration of Helsinki (Seoul 2008) and that it will follow the principles of the ICH Guidelines for Good Clinical Practice 1996. The study protocol and its associated documents will be submitted to the Ethics Committee of the MoH of Cambodia and WHO regional office, Western Pacific Region. The ethics team may visit the study at any time during the course of the study as to ensure that all research process and procedures are completely adhered to that sated in the submitted protocol.

#### 17.1 Pyronaridine-artesunate

This ACT is generally well tolerated, however liver enzyme elevations have been observed after treatment in few African and Asian patients and after retreatment of some healthy Caucasian healthy volunteers. As a result it is recommended that pyronaridine-artesunate be administered not more than once until results from ongoing retreatment studies become available.

# 17.2 Risk of phlebotomy & finger stick

The primary risks of phlebotomy include local discomfort, occasional bleeding or bruising of the skin at the site of needle puncture, and rarely haematoma or infection.

# 17.3 Benefits

Malaria is a disease that needs to be treated promptly. All patients will benefit from receiving efficacious treatment at no cost. They will be followed up closely and will be given rescue treatment if clinically indicated.

# 17.4 Alternatives to Study Participation

Subjects are able to decline freely participation in this study. If so, they will receive standard care for their malaria.

#### 17.5 Incentives & Compensation

Study patients or their guardian in the case of children will be compensated for time lost from work. Patients will be reimbursed the cost of local transport to attend for the follow up visits and will receive a per diem to cover the costs of meals on those days. Each site will determine the amounts in monetary terms. The study will pay for treatment for drug-related SAEs or

other research-related injuries. The study cannot pay for long term care for disability after hospital discharge resulting from complications of the illness.

#### 17.6 Confidentiality

The trial staff will ensure that the participants' anonymity is maintained. Only initials and a study number on the CRF and in the database will identify the participants. All documents will be stored securely and be accessible to trial staff and authorised personnel only.

#### 18 Sample sharing and storage

Samples collected will be used for the purpose of this study as stated in the protocol and stored for future use. Consent will be obtained from subjects for sample storage and/or shipment of specific samples to collaborating institutions for investigations that cannot be performed locally. Any proposed plans to use samples other than for those investigations detailed in this protocol will be submitted to the relevant ethics committees prior to any testing.

